5.2 Exclusion Criteria

If an individual meets any of the following criteria, he or she is ineligible for this study:

General Criteria:

1. Any condition or change during the RECAST SLE study that in the opinion of the Investigator or the Sponsor would interfere with evaluation and interpretation of subject safety or alter the risk-benefit associated with IP administration.
2. Participation in another clinical study with an IP during the RECAST SLE study period.
3. Planned elective surgeries that in the opinion of the Investigator or the Sponsor would interfere with evaluation and interpretation of subject safety.
4. Any herpes zoster, cytomegalovirus, or Epstein-Barr virus infection that was not completely resolved prior to Visit 1.

5. Clinically significant active infection at Visit 1, in the opinion of the Investigator, including ongoing and chronic infection requiring antibiotics or antiviral medication (chronic nail infections are allowed).
6. Pregnant or lactating females.

Prior and Concomitant Therapy Criteria:

7. Receipt of any prohibited medication during the RECAST SLE study period. Receipt of any restricted medications during the RECAST SLE study period must be discussed with the Sponsor's Medical Monitor and agreed upon prior to enrollment into this study.

5.3 Lifestyle Considerations

Subjects must be instructed not to take any medications, including over-the-counter (OTC) or herbal products or ayurvedic medications without first consulting the Investigator. Prohibited and permitted medications are discussed in [Section 6.9](#).

5.4 Screen Failures

A screen failure occurs when a subject who has consented to participate in the clinical study is not subsequently entered/enrolled in the study. A minimal set of screen failure information is required to ensure transparent reporting of screen failure subjects, to meet the Consolidated Standards of Reporting Trials publishing requirements, and to respond to queries from regulatory authorities. Minimal information includes screen failure details, eligibility criteria, and any SAEs.

Individuals who do not meet the criteria for participation in this study (screen failure) may not be rescreened. These subjects will remain in and complete the SFU period of the RECAST SLE study.

5.5 Criteria for Temporarily Delaying Enrollment or Administration of Investigational Product

To allow for the continuous dosing of the subjects, the start of this OLE study should occur immediately after the completion of the RECAST SLE treatment period (ie, first OLE dosing [Day 1] coinciding with Week 48/Visit 14 of the RECAST SLE study). Any exceptions to this enrollment date must be reviewed and approved by the Medical Monitor before any subject is allowed to enroll after the Week 48/Visit 14 of the RECAST SLE study.

6 INVESTIGATIONAL PRODUCT AND CONCOMITANT THERAPY

6.1 Investigational Product Administered

The IP will be administered by study-site staff in the study site. On Day 1 and Week 12, subjects will remain under observation for at least one hour after IP administration. The IP will be provided by the Sponsor. Further details regarding the IP can be found in [Table 3](#).

Table 3 Description of Investigational Product and Dosing

Key Information	Investigational Product
Product name	Daxdilimab
Source of procurement	Horizon Therapeutics
Unit dose strength(s)/Dosage level(s)	200 mg dose, administered as 2 × 1.0 mL SC injections
Route of Administration and frequency	SC, Q12W for 48 weeks (Weeks 0 [Day 1], 12, 24, 36, and 48)
Physical description	The drug product will be provided as a sterile liquid in a 2R glass vial with a nominal fill volume of 1.0 mL of 100 mg/mL.
Dosing instructions	Daxdilimab will be administered by clinic staff trained in best practices for SC administration of treatments. More details on the administration method are described in the study manual.

Q12W = once every 12 weeks; SC = subcutaneous; w/v = weight/volume

The contents of the label will be in accordance with all applicable regulatory requirements.

6.2 Preparation, Handling, Storage, and Accountability

The Investigator or designee must confirm appropriate conditions (eg, temperature) have been maintained during transit for all IP received, and any discrepancies are reported and resolved before use of the IP.

Only subjects enrolled in the study may receive IP, and only authorized site staff may supply, prepare, or administer the IP.

All IP must be stored in a secure, environmentally controlled, and monitored (manual or automated) area in accordance with the labeled storage conditions with access limited to the Investigator and authorized site staff.

The Investigator or authorized site staff is responsible for IP accountability, reconciliation, and record maintenance (ie, receipt, reconciliation, and final disposition records).

Further guidance and information for the final disposition of unused IP are provided in the Pharmacy Manual and [Section 6.2.1.4](#).

6.2.1 Preparation/Storage/Handling

6.2.1.1 Inspection and Storage

Each daxdilimab vial selected for dose preparation should be inspected. Any defects with the IP must be reported immediately to the Sponsor's Quality Assurance Department and the site monitor. The Sponsor's Quality Assurance contact information for reporting product complaints is: [contact]. During the investigation of the product complaint, all IP must be stored at labeled conditions unless otherwise instructed.

Daxdilimab should be stored at 2°C to 8°C (36°F to 46°F). Labels will be prepared in accordance with Good Manufacturing Practice (GMP) and local regulatory guidelines.

Each kit has a unique number that is printed on all labels within the kit (ie, the outer carton label and the label on the vial within the carton).

6.2.1.2 Investigational Product Dose Preparation

Preparation of daxdilimab and preparation of the syringe for SC administration are to be performed by an unblinded pharmacist/IP manager using aseptic technique. The same unblinded pharmacist/IP manager in the RECAST SLE study will perform IP and syringe preparation in this OLE study.

Daxdilimab is supplied as a sterile liquid in a 2R glass vial at a nominal fill volume of 1.0 mL, stoppered with a 13-mm elastomeric stopper, and sealed with flip-off cap overseal. Allow the kits to equilibrate to room temperature about 30 minutes prior to dose preparation.

No incompatibilities between daxdilimab and plastic syringes (ie, polypropylene and polycarbonate) have been observed.

Daxdilimab does not contain preservatives and any unused portion must be discarded. Total in-use storage time from needle puncture of the IP vial to start of administration should not exceed 4 hours at room temperature or 24 hours at 2°C to 8°C (36°F to 46°F). If storage time exceeds these limits, a new dose must be prepared from new vials.

If syringes containing IP have been stored at 2°C to 8°C (36°F to 46°F) for any length of time, they must equilibrate to room temperature for one hour prior to administration to the subject. This one-hour equilibrium period is included in the total room temperature hold time for prepared syringes, which must not exceed 4 hours. DO NOT FREEZE.

A SC dose of 200 mg daxdilimab will be administered over 2 injections. To prepare each injection, withdraw one mL of IP into a 1 mL syringe using a 1½-inch needle. For SC dose administration, a 27G ½-inch needle should be used.

6.2.1.3 Investigational Product Dosing, Administration, and Monitoring

The first day of dosing is considered Day 1. This is an open-label study; therefore, study-site staff, and subject will be unblinded.

The same unblinded pharmacist/IP manager in the RECAST SLE study will perform IP and syringe preparation in this OLE study. The skin surface of the anterolateral thigh, upper outer triceps area, upper buttocks, or abdomen (avoiding a 2-inch [5 cm] radius around the umbilicus) should be prepared with an alcohol wipe and allowed to air dry. The skin will be pinched to isolate SC tissue from the muscle. The needle will be inserted at a 90-degree angle to the skin surface approximately halfway into the SC tissue. The prepared IP will be slowly injected (at least a 5-second duration is recommended per 1 mL syringe) into the SC tissue using gentle pressure. The area should not be massaged after injection. The SC injection site can be changed during the study as per subject preference.

The IP should **not** be administered if it has been at room temperature for more than 4 hours, or if it has been at 2°C to 8°C (36°F to 46°F) for more than 24 hours.

Subjects should be monitored under direct observation for at least 60 minutes after the first and second doses of IP administration or until the subject is stable, whichever is longer. Vital signs should be measured as indicated in [Section 8.3.2](#).

As with any antibody, allergic reactions to dose administration are possible. Therefore, appropriate drugs and medical equipment to treat acute anaphylactic reactions must be immediately available, and study personnel must be trained to recognize and treat anaphylaxis. Guidance for anaphylaxis diagnosis is provided in Appendix 5, [Section 10.5](#).

6.2.1.4 Handling and Disposal

It is preferred that unused IP be destroyed at the study site after accountability and approval to destroy, regardless of whether the study was completed or terminated prematurely, with agreement from the Sponsor.

The Investigator may return any unused vials of daxdilimab to the Sponsor or designee. At the time of return, the Investigator must verify, and the Study Monitor must confirm that unused or partially used study products have been returned and that no study products remain at the site.

6.2.2 Accountability

Study-site staff will maintain a record of the IP received, dispensed, administered, and destroyed (if done at the site). All records will be maintained with controlled access to site, Sponsor, and contract research organization (CRO) staff only. A Study Monitor will perform IP accountability and compliance monitoring during the study. A qualified study-site staff member will only administer the study product to subjects included in this study and according to procedures established in this study protocol. Each administration of study product will be documented and transferred to the electronic case report form (eCRF).

6.3 Assignment to Investigational Product

At the study site, each screened subject in the RECAST SLE study is assigned a subject identifier (SID) during screening that will be used on all subject documentation. Subjects enrolled in the SLE OLE study will retain their SID number from the RECAST SLE study.

No randomization scheme will be used, as all subjects will receive daxdilimab 200 mg Q12W.

6.4 Blinding

This is an open-label study. Subjects and Investigators are aware that the IP is daxdilimab 200 mg Q12W.

6.5 Investigational Product Compliance

Site staff will administer the IP SC at the study site. The dose and date of administration of IP must be recorded in the subject's medical/study record and eCRF. Treatment compliance will be assessed based on this information.

6.6 Dose Modification

Dose adjustment of daxdilimab is not allowed in this study.

6.7 Continued Access to Investigational Product After the End of the Study

After the end of the study, each subject will be treated according to standard clinical practice and local practice, at the discretion of the Investigator.

6.8 Treatment of Overdose or Misuse

Any instance of overdose of IP (suspected or confirmed) must be communicated to the Sponsor ([Section 8.4.10](#)). Any associated AEs or SAEs must also be reported, and their management should be recorded.

6.9 Prior and Concomitant Therapy

Any medication or vaccine (including OTC or prescription medicines, recreational drugs, vitamins, and/or herbal supplements) that the subject is receiving at the time of enrollment or receives during the study must be recorded along with:

- Name and indication
- Reason for use
- Dates of administration including start and end dates
- Dosage information including dose and frequency

Any change to concomitant drugs must also be recorded in the corresponding section of the eCRF.

The Medical Monitor should be contacted if there are any questions regarding concomitant or prior therapy.

6.9.1 Permitted Concomitant Therapy

6.9.1.1 Concomitant Medications and Treatments

All concomitant medications (from Visit 1) taken while the subject is participating in the study will be recorded on the eCRF. Subjects must be instructed not to take any medications, including OTC or herbal products or ayurvedic medications without first consulting the Investigator.

Permitted medications ([REDACTED]) are any medications required per the medical history and not specifically prohibited by the protocol during the clinical study (ie, from Visit 1 to the end of the SFU period). Any such medications prescribed or used should be recorded in the eCRF.

6.9.1.2 Concomitant Medications for Systemic Lupus Erythematosus Standard of Care During the Study

Concomitant standard-of-care medications used during the study are part of the subject's previous SLE treatment and, thus, will not be provided by the Sponsor.

6.9.1.2.1 Immunosuppressants

These medications, if given during the RECAST SLE study, must remain stable during the treatment period except for oral glucocorticoid (OGC) and nonsteroidal anti-inflammatory drugs (NSAIDs), which can be adjusted as long as doses are consistent with the parameters as indicated in Sections [6.9.1.2.2](#) and [6.9.1.2.3](#), respectively. Background therapy may only be changed for documented safety issues. The toxicity/event must be confirmed as a documented AE. The dose can be returned to the OLE baseline (Day 1) level if the toxicity/event resolves and if clinically indicated. Initiation of any new immunosuppressant or immunomodulator therapy or increase in

dose above the level used on Day 1 of the OLE may result in withdrawal of the subject from the IP (per Sponsor's Medical Monitor discretion).

6.9.1.2.2 Glucocorticoids

Oral GCs are permitted but not required for participation in the study. Oral GCs other than prednisone may be used orally (PO) at equivalent doses (refer to Appendix 7, [Section 10.7](#)). It is strongly encouraged that Investigators taper the OGC dose as much as tolerated after a subject enrolls into the study, as a goal of this OLE is to determine the lowest clinically appropriate level of steroids, including steroid discontinuation, by Week 36 that can be provided while maintaining responses. Guidance for taper and bursts is outlined below. During the study, Investigators may reach out to discuss any taper or burst scenario with the Medical Monitor as needed.

Oral Glucocorticoid Tapering Guidance

Oral GC tapering must be started by Week 4 of the clinical study.

An example of a suggested OGC tapering regimen is provided in Appendix 8, [Section 10.8](#) as guidance for Investigators. However, due to variability in subject responses to OGC treatment and tolerability of taper, Investigators will have flexibility in how the OGC dose is reduced at each visit, however, it is encouraged that Investigators taper each month by at least 1 mg/day.

OGC tapering must be attempted unless at least one of the following criteria are met:

1. There are new or worsening organ system(s) affected by SLE.
2. There is an increase in skin involvement.
3. There is new or worsening joint involvement.

If there are scenarios outside these listed criteria in which the Investigator deems tapering not appropriate, then the Medical Monitor must be notified and the reason for not tapering will be discussed. All reasons for not tapering **must be** well documented within the EDC.

Glucocorticoid Burst Guidance

We encourage Investigators to limit the use of GC bursts throughout the clinical study as clinically feasible. GC bursts are allowed at the Investigators discretion. The reason for a GC burst and regimen prescribed **must be** well documented in the EDC.

Increase in Oral Glucocorticoids for Surgery and Prevention of Adrenal Insufficiency

Increases in OGCs for surgery and prevention of adrenal insufficiency are allowed as clinically indicated.

6.9.1.2.3 Other Permitted Medications

For all enrolled subjects, additional treatments given to subjects with SLE are permitted during the study as follows:

- Angiotensin-converting enzyme inhibitors and angiotensin receptor blockers:
 - If used during the RECAST SLE study, it is recommended that they be maintained at a stable dose during the OLE study, unless dose change, discontinuation, or initiation is required for documented safety reasons.

- Anti-COVID therapeutic antibodies
 - If used during the study, the Medical Monitor must be notified immediately, and continuation of IP will be determined on a case-by-case basis.
- Aspirin
 - Low-dose aspirin (\leq 350 mg/day) may be used for cardiovascular prophylaxis; this is permitted in addition to use of NSAID as specified below.
- Osteoporosis prophylaxis and treatment
 - Vitamin D and calcium supplementation, and if necessary, treatment of osteoporosis is allowed according to local standard-of-care guidelines. These medications will not be supplied by the Sponsor.
- Herbal supplements
 - May be continued during the study. It is strongly recommended that the dosages and preparations remain stable unless discontinued all together. It is recommended that no herbal supplements be initiated or reinitiated once discontinued during the study.
- Medications for the treatment of injection site reactions:
 - These are allowed and may include topical or systemic antihistamines, topical GCs, paracetamol, or NSAIDs.
- NSAIDs
 - NSAIDs can be used as needed (PRN) during the OLE (not exceeding local guidelines).
 - Subjects taking a NSAID (including cyclooxygenase 2 inhibitors; topical, prescription, or OTC) on a regular schedule for SLE symptoms at the OLE baseline (Day 1) can continue to do so throughout the study at a stable dose.
 - NSAIDs should not be taken on visit days until all assessments are complete. Subjects may have the dose adjusted during the study for documented toxicity/safety reasons.
 - Any NSAIDs (whether prescription, OTC, or topical) should not be used above the maximum allowable doses per local guidelines, and site should perform regular AE monitoring of these concomitant medications.
- Opioids
 - Up to 40 mg/day morphine-equivalent are permitted at a stable dose if present at the OLE baseline (Day 1). Initiation of opioids and/or PRN dosing of opioids after Day 1 of the OLE for SLE is discouraged and should not exceed 40 mg/day or equivalent if prescribed. These may be titrated off as tolerated during the study. Analgesics, including opiates, may be used at stable doses or PRN for temporary relief of symptoms not due to SLE, but then are strongly recommended to be avoided 24 hours prior to each study visit.
- Acetaminophen (paracetamol)

- Short acting acetaminophen (paracetamol) may be initiated or continued for pain control during the study at approved doses. Pain medications should not be used within a minimum of 6 to 12 hours (based on known duration of effect) of a scheduled visit.
- Topical therapy for CLE
 - Concurrent use of topical therapy for CLE (eg, GCs, pimecrolimus) is permitted. Topical therapy must be the same being used in the 2 weeks prior to the OLE baseline (Day 1), and the dose and frequency of application must be stable. During the study, topical therapy may be reduced or discontinued based on clinical manifestations and Investigator discretion. Should cutaneous skin manifestations reoccur, the same topical therapy may be resumed up to the dose used at the OLE baseline (Day 1). New dermatologic preparations may be used for the duration of the study if needed. It is also recommended that subjects use sunscreen (list as concomitant medication for SLE) and avoid sun exposure during the study. Topical moisturizers are also permitted.

Any medications (other than those prohibited by the protocol) that are considered necessary for the subjects' welfare and will not interfere with the study medication may be given at the Investigator's discretion.

6.9.2 Prohibited Concomitant Medications

The treatments and therapies listed in Section 6.9.3 will not be permitted from Day 1 of the OLE until the end of the study (with exceptions as noted for those therapies that are potentially permitted per [Section 6.9.1](#)).

6.9.3 Medications and Therapies That Lead to Immediate Discontinuation of Investigational Product

The following therapies are prohibited from Day 1 of the OLE through end of the study. These medications are also excluded as per the inclusion and exclusion criteria ([Section 5](#)) and during the study:

- Biologic immunomodulators (including but not limited to belimumab, abatacept, or rituximab)
- Bone marrow, stem cell (eg, mesenchymal stem cells), or solid organ transplant
- Cyclophosphamide
- GCs
 - Intralesional
 - Intradermal for alopecia
 - Adrenocorticotropic hormone (ACTH) analogs (eg, Acthar[®], Synacthen[®])
 - dehydroepiandrosterone
 - Topical use (may be allowed per the permitted medications; see [Section 6.9.1.2.3](#)) if they are used in accordance with inclusion and exclusion criteria ([Section 5](#)).
- Ig therapy (for anti-COVID therapeutic antibodies, see [Section 6.9.1.2.3](#)).
- Investigational agents

- IPP-201101 (Lupuzor™)
- IV corticosteroids > 1 g methylprednisolone or equivalent
- Janus kinase inhibitors (eg, tofacitinib [Xeljanz®], baricitinib [Olumiant®], upadacitinib [Rinvoq™], filgotinib, peficitinib)
- Live or attenuated vaccines, including Bacille-Calmette-Guerin (the Sponsor recommends that Investigators ensure all subjects are up to date with required vaccinations prior to entry into the study)
- Minocycline
- Plasmapheresis, plasma exchange, or Therakos® photopheresis
- Thalidomide and thalidomide derivatives (eg, lenalidomide [Thalomid®, Revlimid®])
- Topical calcineurin or mammalian target of rapamycin (mTOR) inhibitors (eg, pimecrolimus [eg, Elidel®], sirolimus)
- Sulfasalazine
- Systemic mTOR inhibitors (eg, sirolimus [Rapamune®])

[figure not shown]

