6.9.4 Restricted Medications

As daxdilimab is an investigative immunomodulatory agent, non-protocol-permitted changes to immune modifiers or immunosuppressants on study are strongly discouraged.

If a subject starts any of the following during the treatment period or increases the dose above the OLE baseline (Day 1) dose, the Investigator must notify the Sponsor's Medical Monitor immediately. The Medical Monitor will determine if the subject may continue to receive IP.

- Antimalarials:
 - Chloroquine
 - Hydroxychloroquine
 - Quinacrine
- AZA
- Cyclosporine
 - Cyclosporine eye drops are permitted for use while on study.
 - Lifitegrast ophthalmic solution (Xiidra eye drops) are permitted for use while on study.
- Danazol
- Dapsone
- GCs
 - Intramuscular > 80 mg/day methylprednisolone or equivalent.
 - Intra-articular/tendon sheath/bursal injections of total methylprednisolone > 80 mg or equivalent.
 - IV > 40 mg/day but ≤ 1 g/day methylprednisolone or equivalent.
 - OGC
 - > 40 mg/day prednisone or equivalent.
 - Treatment above the OLE baseline (Day 1) dose for a dosing period of > 14 days.
 - Long biologic half-life (eg, dexamethasone, betamethasone).

- SC or intramuscular precursors (eg, ACTH).
- Intra-articular medications other than GCs
- Leflunomide
- 6-Meaptopurine (6-MP)
- MPA
- MMF
- MTX or any change in the route of administration of PO, SC, or intramuscular MTX
- Sulfasalazine
- Tacrolimus
- Voclosporin

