7.1 Discontinuation of Investigational Product

An individual subject will not receive any further IP if any of the following occur in the subject:

- Receipt of any medications or therapies in [Section 6.9.3](#).
- A Grade 3 or higher allergic reaction to the IP.
- A Grade 3 or higher infection considered related to the IP.
- Other AE that contraindicates further dosing in the opinion of the Investigator and/or the Sponsor, Medical Monitor, and/or the SDMC.
- Withdrawal of consent from further treatment with IP.
- Subject is determined to have met one or more of the exclusion criteria or failed to meet all the inclusion criteria for study participation and there is a potential safety risk associated with continuation identified upon consultation with the Medical Monitor.
- Pregnancy or a decision to become pregnant.
- Any of the following liver function abnormalities:
 - Alanine aminotransferase (ALT) or aspartate aminotransferase (AST) $\geq 8 \times$ upper limit of normal (ULN).
 - ALT or AST $\geq 5 \times$ ULN for more than 2 weeks.
 - ALT or AST $\geq 3 \times$ ULN and total bilirubin $\geq 2 \times$ ULN or international normalized ratio ≥ 1.5 without alternative explanation.
 - ALT or AST $\geq 3 \times$ ULN with the appearance of fatigue, nausea, vomiting, right upper quadrant pain or tenderness, fever, rash, and/or eosinophilia ($\geq 5\%$).

Subjects who permanently discontinue IP at any point but who **do not** withdraw consent of study participation will complete the Study Week 48/ET visit as soon as possible after IP discontinuation and then enter SFU period unless the subject withdraws consent of study participation (as described in Section 7.2) or the subject is lost to follow-up (Section 7.3).

Appendix 4, [Section 10.4](#) describes the process to be followed to identify and appropriately report potential Hy's Law cases and Hy's Law cases.

Follow the SoA ([Table 1](#)) for data to be collected at the time of discontinuation of IP and follow-up and for any further evaluations that need to be completed.

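### Sulfasalazine falls under both a mandatory stop of investigational product and a Medical Monitor discretion; the ACTH entries overlap, and the status of topical pimecrolimus is unclear

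*Protocol*

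**What the plan says.** Protocol 6.9.3 lists therapies that lead to immediate discontinuation of IP and opens with "The following therapies are prohibited from Day 1 of the OLE through end of the study". It adds that these therapies are also excluded through the Section 5 criteria. Section 7.1 enforces the list: "An individual subject will not receive any further IP if any of the following occur in the subject", and the first trigger is "Receipt of any medications or therapies in" 6.9.3.

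Protocol 6.9.4 is a separate list of restricted medications. Its rule applies if a participant "starts any of the following during the treatment period or increases the dose above the OLE baseline (Day 1) dose". The Investigator must then notify the Medical Monitor at once, and "The Medical Monitor will determine if the subject may continue to receive IP".

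Section 6.9.2 bars the 6.9.3 therapies from Day 1 to the end of the study, "with exceptions as noted for those therapies that are potentially permitted per" Section 6.9.1.

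The three agents appear as follows.

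- **Sulfasalazine:** a bare bullet in 6.9.3 and again in 6.9.4.
- **ACTH:** "Adrenocorticotropic hormone (ACTH) analogs" in 6.9.3, and "SC or intramuscular precursors (eg, ACTH" (closing bracket omitted here) in 6.9.4.
- **Pimecrolimus:** an example of permitted topical therapy for cutaneous lupus in 6.9.1.2.3, and an example of a prohibited topical calcineurin inhibitor in 6.9.3.

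**The concern.** The two lists carry different consequences. An entry in 6.9.3 ends dosing through 7.1, whereas an entry in 6.9.4 opens a decision by the Medical Monitor. An agent on both lists, with nothing to separate the entries, cannot be handled as written. If 7.1 prevails, the 6.9.4 entry has no effect, and a Medical Monitor who relied on it would allow a dose that 7.1 forbids. If 6.9.4 prevails, 7.1 is not followed.

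This matters for the analysis because permanent discontinuation sends the participant to the Week 48/ET visit and then into the 8-week safety follow-up. That can shorten both exposure and observation time for the primary adverse event endpoint. The same event, handled differently at different sites, would also be counted differently in these SAP summaries:

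- treatment discontinuation with reasons (SAP 4.5);
- exposure and person-years (SAP 4.6);
- major protocol deviations (SAP 4.2);
- rescue medication, which SAP 4.9.4 defines partly through whether a new treatment is permitted.

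**Working it through.** **Text comparison**

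| Agent | 6.9.1 (permitted) | 6.9.3 with 7.1 (IP stops) | 6.9.4 (Medical Monitor decides) | Reading |
|---|---|---|---|---|
| Sulfasalazine | not named in the visible text | listed, no qualifier | listed, no qualifier | direct contradiction |
| ACTH products | not named in the visible text | analogs, no route given | SC or intramuscular precursors, ACTH as the example | overlap, no boundary between the lists |
| Topical pimecrolimus | named as permitted (6.9.1.2.3) | named, no cross-reference | not listed | ambiguous |

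*Sulfasalazine.* A new start meets the 6.9.3 prohibition and the 6.9.4 trigger together. Two possible ways out fail.

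- The 6.9.2 exception points only to 6.9.1 and says nothing of 6.9.4.
- Section 6.9.1.2.1 gives the Medical Monitor a general discretion over new immunosuppressants. If that counted as permission, it would also reach cyclophosphamide and the Janus kinase inhibitors and would largely empty 6.9.3. Section 6.9.1.1 in any case limits permitted medications to those the protocol does not specifically prohibit.

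The 6.9.4 trigger also covers an increase over the Day 1 dose, which presupposes use on Day 1, whereas 6.9.3 prohibits its items from Day 1.

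*ACTH.* The terms differ, so this is not a verbatim duplicate. Section 6.9.4 gives a route, but 6.9.3 gives no matching limit, so an injected ACTH product can fall under either entry. The protocol does draw such lines elsewhere: IV corticosteroids above 1 g methylprednisolone are in 6.9.3, and those above 40 mg/day up to 1 g/day are in 6.9.4.

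*Pimecrolimus.* The 6.9.2 exception can be read to cover the use that 6.9.1.2.3 permits. However, the 6.9.3 entry lacks the pointer to 6.9.1.2.3 that the topical glucocorticoid and immunoglobulin entries carry, and 7.1 states no exception. For a new start, 6.9.1.2.3 is itself unclear. It requires topical therapy to be the same as in the 2 weeks before Day 1, and then allows new dermatologic preparations if needed.

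**Size per affected participant**

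The plan gives no figure to reproduce. The inputs are the scheduled dose days 1, 85, 169, 253 and 337 (Protocol Table 1), the duration rule in SAP 4.6, about 156 eligible participants, and 195 randomized in RECAST SLE (Protocol 9.5).

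Duration = last dose day + 28 − first dose day + 1. The minus sign is missing from the extracted SAP text and is assumed. Person-years = duration / 365.25.

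| Last dose received | Duration (days) | Person-years | Loss against five doses |
|---|---|---|---|
| 1 (Day 1) | 1 + 28 − 1 + 1 = 29 | 0.079 | 336/365.25 = 0.92 |
| 2 (Day 85) | 85 + 28 − 1 + 1 = 113 | 0.309 | 252/365.25 = 0.69 |
| 3 (Day 169) | 169 + 28 − 1 + 1 = 197 | 0.539 | 168/365.25 = 0.46 |
| 4 (Day 253) | 253 + 28 − 1 + 1 = 281 | 0.769 | 84/365.25 = 0.23 |
| 5 (Day 337) | 337 + 28 − 1 + 1 = 365 | 0.999 | 0 |

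One participant is 1/156 = 0.64 percentage points. On the full analysis set, which SAP 4.5 uses for disposition and which cannot exceed 195, one participant is at least 1/195 = 0.51 points.

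**The case against.** The case against accepts the sulfasalazine duplication and disputes the weight of the rest.

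- **Pimecrolimus is largely covered.** Section 6.9.2 exempts therapies permitted under 6.9.1, and 6.9.1.2.3 names pimecrolimus. This stands for continued use. What remains is the status of new starts and a missing cross-reference.
- **ACTH is not the same kind of conflict.** This stands as to wording, since only sulfasalazine is duplicated word for word. The consequence is still the same, because one entry stops IP and the other leaves a decision.
- **The Day 1 argument is thin.** The dose-increase clause introduces the whole 6.9.4 list and was not written for sulfasalazine. Whether any participant could be taking sulfasalazine on Day 1 depends on the RECAST SLE medication lists, which are not in the documents. This stands, so the finding rests on new starts. The same limit applies to exclusion criterion 7, which is affected only if those lists contain the same overlap.
- **A redaction sits inside the permitted-medication sentence of 6.9.1.1.** This is fair to note but unlikely to matter, because that sentence excludes specifically prohibited drugs.
- **The effect is small.** The largest single loss, 0.92 person-years, is about 0.6% of 156 × 0.999 ≈ 156 person-years. The study is descriptive with no formal hypothesis, and participants who stop IP without withdrawing consent still have an ET visit and follow-up. This stands, but it does not make the rule workable.
- **There are safeguards.** The Medical Monitor must be notified immediately, and deviations are reviewed before database lock. Both limit unnoticed divergence between sites, but neither says which rule applies.

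**Conclusion.** The concern holds. For sulfasalazine the protocol gives two incompatible instructions on whether dosing continues, and no exception in the visible text reconciles them. The ACTH entries overlap with no stated boundary. Topical pimecrolimus is ambiguous, mainly for new starts. Confidence is high for sulfasalazine, and the other two are weaker points of the same kind.

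The total size is unknown because the documents give no number of users. The per-participant figures assume dosing on the scheduled days, the SAP 4.6 formula read with the minus sign, and a denominator of about 156 (or at most 195 for disposition). No hypothesis test is affected. At stake are the consistent application of an IP-stopping rule and the counts that follow from it. It should be corrected.

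**What to change.** Reconcile Protocol 6.9.1.2.3, 6.9.2, 6.9.3, 6.9.4 and 7.1 so that each agent has one status:

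1. List sulfasalazine once.
2. Merge the two ACTH entries or state the boundary between them.
3. State at the 6.9.3 pimecrolimus entry whether the 6.9.1.2.3 permission applies and whether it extends to new starts. Settle the two statements on new topical preparations within 6.9.1.2.3.
4. Have the 7.1 trigger recognise the exceptions stated in 6.9.2 and 6.9.3.

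The status of each agent is for the sponsor to decide on clinical grounds.

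The change is clarification wording, with no new data collection and no change to the SAP's methods. It is still a protocol amendment. Under Protocol 10.1.1 it needs IRB/IEC approval, and health authority approval as well if it is judged substantial.
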